5.7.2. Secondary Efficacy Analyses

Responder outcome will also be analyzed at the Day 5 visit. A 2-sided 95% CI for the observed difference in the responder rate at the Day 5 visit will be calculated for the micro-ITT population using the same method as for the primary efficacy analysis.

The number and percentage of subjects in each treatment group with an outcome of clinical cure, clinical failure and indeterminate/missing (by definition the CE and ME populations do not include subjects with an indeterminate/missing response) will be presented for the following time points and analysis populations:

- Day 5 - ITT, CE-Day 5, micro-ITT, micro-MITT, ME-Day 5 populations
- EOI Visit - ITT, CE-EOI, micro-ITT, micro-MITT, ME-EOI populations
- EOT Visit – ITT, CE-EOT, micro-ITT, micro-MITT, ME-EOT populations
- TOC Visit – ITT, CE-TOC, micro-ITT, micro-MITT, ME-TOC populations
- FU Visit – ITT, CE-FU, micro-ITT, micro-MITT, ME-FU populations

Two-sided 95% unadjusted CIs will be constructed for the observed difference in the clinical cure rates between the treatment groups for descriptive purposes; no conclusion of NI will be made. Analyses at the TOC visit will also be presented by primary infection site and receipt of a single dose of effective non-study antibiotics in the ITT and CE-TOC populations.

Per-subject microbiological response will be summarized as success, failure and indeterminate at the Day5, EOI, EOT, TOC and FU visits in the micro-ITT, micro-MITT and ME populations. Two-sided 95% unadjusted CIs will be constructed for the observed difference in the success rates between the treatment groups for descriptive purposes; no conclusion of NI will be made.

Time to resolution of signs and symptoms is defined as the number of days from the start of study treatment to the visit where all signs and symptoms are reported as absent or have at least a 2-grade decrease in severity (chills, rigor or warmth associated with fever or hypothermia, flank or pelvic pain, nausea or vomiting, dysuria, urinary frequency or urinary urgency, costo-vertebral angle tenderness on physical examination). Subjects who discontinue the study prior to having all signs and symptoms resolved will be censored at the last evaluation at which sign and symptoms were assessed.

Time to resolution of signs and symptoms will be analyzed using Kaplan-Meier methods in the micro-ITT population. The median, 25th and 75th percentile will be presented by treatment group and Kaplan-Meier curve will be presented by treatment group.

5.7.3. Additional Efficacy Analyses

5.7.3.1. Intravenous Only Responder Outcome

Responder outcome will be analyzed at the EOT, TOC and FU visits in the micro-ITT population among subjects who only received IV study drug and did not transition to PO study drug for any reason (including treatment failures who did not receive PO study drug). The analysis will be conducted using the same methods as the primary efficacy analysis.

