7.4 Dosing Rationale

For this phase 3 study in subjects with cUTI, the eravacycline dose selected is 1.5 mg/kg q24h IV. The justification for this dose is presented below.

The 1.5 mg/kg IV dose was selected based upon the favorable efficacy and safety profile observed in the phase 2 study in cIAI. Data from the phase 2 study was used in a Monte Carlo simulation and the predicted probability of clinical success for this dose of eravacycline was >80% for all pathogens with an minimum inhibitory concentration (MIC) value of 4 µg/mL or less. An analysis of data from subjects who received only IV treatment in the phase 3 study in cUTI also supports the selection of 1.5 mg/kg IV.

The 1.5 mg/kg IV dose of eravacycline also results in urine levels at steady state well over the MIC₉₀ values for all pathogens except *Pseudomonas aeruginosa*. In the phase 1 IV MAD study the urine concentrations of eravacycline following the first dose in the 1.5 mg/kg q24h group were 6.92 ± 1.16 µg/mL for the first 8 hours post-dose and 2.83 ± 1.8 µg/mL for the next 16 hours. This suggests that high drug concentrations are initially delivered that are greater than the highest MIC₉₀ observed in the Gram-negative surveillance panels, and 4- to 8-fold higher for most common Gram-negative and Gram-positive pathogens in cUTI. By steady-state, the trough values were 9.19 ± 4.97 µg/mL, suggesting that values remain at least 2- to 4-fold the highest MIC₉₀ values for Gram-negative pathogens.

The comparator, ertapenem, was chosen as it is a recommended treatment for cUTI according to clinical practice guidelines and is approved by the Food and Drug Administration (FDA) and other regulatory authorities for the treatment of cUTI. Ertapenem will be given at 1 g IV q24h.

Both eravacycline and ertapenem will be administered for a minimum of 5 doses, in accordance with FDA guidance for an investigational drug with only an IV formulation. After 5 doses, subjects may transition to levofloxacin 750 mg PO QD if they meet clinical criteria and do not have a levofloxacin-resistant baseline pathogen or documented allergy to levofloxacin (See Section 11.3.2). Levofloxacin was chosen as the PO transition for both treatment groups as it is

approved by the FDA and other regulatory authorities and is widely used for the treatment of cUTI.

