11.3.2 Guidance to Investigators for IV-to-PO Transition

An IV-to-PO transition may occur after Day 5 (according to the instructions in Section 11.3.1) provided the subject has demonstrated adequate clinical improvement.

Adequate clinical improvement for an IV-to-PO transition is defined as follows:

- Subject must have adequate appetite and food intake
- Subject must be afebrile for at least 24-h
- Subject must have documented significant improvement or resolution of signs and symptoms present at screening

If the subject qualifies for IV-to-PO transition the Investigator should choose a PO antibiotic as follows:

- If a baseline pathogen was identified and was susceptible to levofloxacin, no baseline pathogen grew, or no antibiotic susceptibility results are available, levofloxacin should be chosen as the PO antibiotic
- If a baseline pathogen was identified and was not susceptible to levofloxacin, or the subject has a documented allergy to levofloxacin, an appropriate alternative PO antibiotic should be chosen, as described in the Pharmacy Manual, OR
- If no appropriate alternative PO antibiotic is available, the subject should continue IV study drug for the entire duration of therapy

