Failure	Indeterminate / Missing	Non-responder
Indeterminate / Missing	Success	Indeterminate
Indeterminate / Missing	Failure	Non-responder
Indeterminate / Missing	Indeterminate / Missing	Indeterminate

For the micro-ITT population, the proportion of micro-ITT subjects with a response is defined using the following formula (where the denominator adds to the total number of subjects in the micro-ITT population):

Number of subjects with response

(Number of subjects with a response + Number of subjects with a non-response + Number of subjects with an indeterminate response)

The primary efficacy analyses will be based on the micro-ITT population. The NI test will be a one-sided hypothesis test performed at the 2.5% level of significance. This NI test will be based on the lower limit of the two-sided 95% confidence interval (CI) for both EOI and TOC Visits. The primary efficacy outcome is the percentage of subjects with an outcome of responder (clinical cure and microbiological success) at the EOI and TOC Visits. The primary analysis is unadjusted.

The number and percentage of subjects in each treatment group defined as a responder, non-responder and indeterminate/missing will be tabulated. The null and alternative hypotheses are as follows:

$$H_0: p_1 - p_2 \leq -\Delta \text{ and } H_1: p_1 - p_2 > -\Delta$$

Where p_1 is the responder rate in the eravacycline treatment group, p_2 is the responder rate in the ertapenem treatment group, and Δ is the NI margin of 10%. Note: For H_0 , outcomes at both EOI and TOC visits will be considered. For H_1 , outcomes at EOI or TOC visits will be considered.

To test the null hypothesis, two-sided 95% CIs for the observed difference in responder rates (eravacycline treatment group minus ertapenem treatment group) will be calculated for the micro-ITT population for the EOI and TOC Visits. If the lower limit of both (EOI and TOC Visits) 95% CIs for the difference in responder rates in the micro-ITT analysis set exceeds – 10%, then the null hypothesis will be rejected and the NI of eravacycline to ertapenem will be declared.

The two-sided 95% CIs for NI testing based on the difference of responder rates at the EOI and TOC Visits, will be computed using the method proposed without stratification by Miettinen and Nurminen (Miettinen 1985). For notation purposes, assume 1 represents the eravacycline group (Group 1) and 2 represents the ertapenem group (Group 2).

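### The IV-only comparison in SAP 5.7.3.1 selects subjects after randomization and borrows the primary methods without a descriptive-only limit

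*SAP*

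**What the plan says.** SAP 5.7.3.1 analyses responder outcome at EOT, TOC and FU in micro-ITT subjects selected as follows: "among subjects who only received IV study drug and did not transition to PO study drug for any reason". The selection is stated to be "including treatment failures who did not receive PO study drug". On method it says: "The analysis will be conducted using the same methods as the primary efficacy analysis". In SAP 5.7.1 those methods are the difference in responder rates, the unstratified Miettinen-Nurminen two-sided 95% CI, and a one-sided 2.5% non-inferiority test against -10%.

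Protocol 11.3.2 governs the switch. "An IV-to-PO transition may occur after Day 5", subject to three conditions: "Subject must have adequate appetite and food intake"; "Subject must be afebrile for at least 24-h"; and documented improvement or resolution of the screening signs and symptoms. A subject whose pathogen is not susceptible to levofloxacin, or who is allergic to it, takes another oral drug, and stays on IV study drug only if there is no suitable one.

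SAP 5.7.2 labels its CIs for clinical cure and microbiological success descriptive and rules out any non-inferiority conclusion from them. SAP 5.7.3.1 contains no such sentence. Protocol 15.2.1 does not mention the IV-only analysis.

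Protocol 7.3.6 reports, as a post hoc result, that outcomes in subjects of the earlier cUTI study who did not switch appeared to favour eravacycline. Protocol 7.4 cites the same kind of subset for the dose: "An analysis of data from subjects who received only IV treatment in the phase 3 study in cUTI also supports the selection".

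**The concern.** Staying on IV is an event after randomization, and two of its causes, poor response and poor tolerability, can be effects of the assigned drug. If the drugs differ in how often they keep subjects from meeting the switch criteria, the IV-only groups contain different kinds of patient. Analysing them as randomized (SAP 5.7) does not restore comparability once selection has taken place.

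The subset is also attractive, because it looks like a test of the IV drug without levofloxacin. The sponsor has already drawn on this kind of subset once. A difference printed with the primary analysis's CI and no stated limit may be read as comparative evidence when the gap reflects only who was left on IV.

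**Working it through.** **Method that is borrowed.** The documents give no size, composition or power for the IV-only group, so there is no figure of that analysis to reproduce. The primary design does reproduce. Farrington-Manning at 71% vs 72%, margin 10% and one-sided 0.025 gives 395 per arm and 80.1% power (SAP Table 3: 790 in total, 80.0%). At EOI, 93% vs 94%, power is 99.8% (stated as >99%).

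**Illustration with no drug effect.** Each subject is given the same TOC outcome on either drug, with 72% overall in both arms. Only membership of the IV-only group may differ. All of the following are assumptions, with 395 micro-ITT subjects per arm:
- a share s of each arm (10%, 20% or 30%) stays on IV and responds at 60%;
- 6% of each arm are failures who stay on IV, with 0% response;
- a further share d stays on IV in one arm only.

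*Scenario A: the extra subjects are on eravacycline and respond at 72%.* Ertapenem rate = 0.60s/(s + 0.06). Eravacycline rate = (0.60s + 0.72d)/(s + 0.06 + d). I take d from 2% to 14.9%. The upper end is a ceiling, the whole nausea gap in the earlier cUTI study (18.0% - 3.1%, Protocol 7.3.6). The 7.4% is the gap in the phase 3 cIAI study (8.1% - 0.7%, Protocol 7.3.5).
- s = 30%, d = 2%: 0.1944/0.38 = 51.2% vs 0.18/0.36 = 50.0%, difference +1.2.
- s = 20%, d = 7.4%: 0.1733/0.334 = 51.9% vs 0.12/0.26 = 46.2%, difference +5.7 (95% CI -7.2 to 18.4). The lower limit is above -10%.
- s = 10%, d = 14.9%: 0.1673/0.309 = 54.1% vs 0.06/0.16 = 37.5%, difference +16.6 (1.4 to 30.8).

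*Scenario B: the extra eravacycline subjects are early stoppers who respond at 30%, with a common 1% of such subjects in both arms.* I take d from 2% to 10%.
- s = 10%, d = 2%: 0.069/0.19 = 36.3% vs 0.063/0.17 = 37.1%, difference -0.7.
- s = 20%, d = 10%: 0.153/0.37 = 41.4% vs 0.123/0.27 = 45.6%, difference -4.2.

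*Scenario C: as A, but the extra subjects are on ertapenem.* Here d = 4.8%, the phase 2 nausea gap (6.7% - 1.9%, Protocol 7.3.4).
- s = 10%: 0.06/0.16 = 37.5% vs 0.0946/0.208 = 45.5%, difference -8.0.
- s = 20%: 0.12/0.26 = 46.2% vs 0.1546/0.308 = 50.2%, difference -4.0.
- s = 30%: 0.18/0.36 = 50.0% vs 0.2146/0.408 = 52.6%, difference -2.6.

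The true difference is zero throughout. The apparent one runs from -8.0 to +16.6 points.

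**Precision.** Even with no selection bias, an IV-only group of 10% to 40% of 395 (40 to 158 per arm) has 14% to 43% power for a 10% margin at 71% vs 72%.

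**The case against.** **No non-inferiority claim is announced.** A reader might infer from the reference to the primary methods that non-inferiority will be declared in this subgroup. The SAP does not say so. The rule in 5.7.1 needs both EOI and TOC, while the IV-only analysis is at EOT, TOC and FU, so the rule cannot be carried over as written. The analysis is listed as additional and has no alpha. This objection stands: the fault is a missing limit.

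**The direction of bias is not known.** A reader might infer that nausea must tilt the result towards eravacycline. In phase 2, the only study the protocol describes with this dose against ertapenem, nausea was 1.9% with eravacycline and 6.7% with ertapenem, although emesis was 5.7% vs 0% (Protocol 7.3.4). The 8.1% vs 0.7% comes from another regimen, and the 18.0% vs 3.1% from a study with oral eravacycline against levofloxacin. This also stands.

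**Some routes in are harmless.** Levofloxacin resistance or allergy without an oral alternative is fixed at baseline. That is true, but the subgroup mixes these subjects with the others.

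**The CI is useful.** It shows how imprecise the subset is, so it need not be removed.

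**A clean comparison already exists.** EOI responder outcome in the full micro-ITT population is co-primary, EOI is within 1 day of the last IV dose, and oral drug follows EOI (Protocol 9.2). That stands and belongs in the fix. It does not make the IV-only contrast interpretable.

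**Conclusion.** The point holds as a limited one. The IV-only group is selected by events after randomization that the assigned drug can influence, and 5.7.3.1 lacks the limit that 5.7.2 sets on less vulnerable comparisons. The difference and CI should not be read as a drug effect. They would estimate one, in subjects who would stay on IV under either drug, only if the assigned drug did not affect the switch. The documents do not argue this.

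The range of -8.0 to +16.6 points rests on assumed subgroup shares and response rates. It shows that sign and size depend on who stays on IV; it does not forecast this trial. The primary conclusion is not affected.

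Two further inferences are not supported. The sentence in Protocol 7.4 does not undo the dose choice: it concerns an earlier study and sits beside phase 2 and simulation data. The levofloxacin-resistant subgroup (SAP 5.7.3.2) is not a clean substitute, although it is defined at baseline, because those subjects may receive another oral antibiotic (Protocol 11.3.1 and 11.3.2) and their TOC outcome still includes oral therapy.

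**What to change.** Amend SAP 5.7.3.1 to state that:
1. IV-only responder rates by arm are descriptive, any CI is given only to show precision, and no non-inferiority, superiority or causal conclusion will be drawn;
2. the IV-only group will be tabulated by arm using items already collected: premature discontinuation of study drug and its reason (SAP 5.1), clinical failure (5.7.1) and baseline levofloxacin resistance (5.4);
3. the between-arm inference on IV therapy before the oral switch is the co-primary EOI responder outcome in the full micro-ITT population (5.7.1).

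The split uses existing items because the EOI procedures in Protocol 11.2.5 list no recorded reason for staying on IV. A split by that reason might need a change to the case report form.

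The cost is a few lines of text and one table. The downside is that the IV-only result can no longer be cited as a comparative efficacy claim. EOI also does not show what TOC response would have been without oral drug; that question would need its own estimand and stated assumptions.

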5.7.3.2. Responder Outcome in Subjects with and without Levofloxacin-Resistant Baseline Pathogens

Responder outcome will be analyzed at the EOI and TOC visits in subjects with levofloxacin-resistant baseline pathogens. A 2-sided 95% CI for the observed difference in the responder rate at the EOI and TOC visits will be calculated for the micro-ITT population using the same method as for the primary efficacy analysis.

5.7.3.3. Responder Outcome in Subjects with and without Ertapenem-Resistant Baseline Pathogens

Responder outcome will be analyzed at the EOI and TOC visits in subjects with ertapenem-resistant baseline pathogens. A 2-sided 95% CI for the observed difference in the responder rate at the EOI and TOC visits will be calculated for the micro-ITT population using the same method as for the primary efficacy analysis.

5.7.3.4. Clinical Outcome Measures

A summary (number and percentage of subjects) of the shift from baseline to each visit (Day 5, EOI, EOT, TOC and FU Visits) in the signs and symptoms of cUTI will be presented by treatment group for the micro-ITT population.

5.7.3.5. Microbiological Outcomes

Microbiologic response by baseline pathogen will be determined as the proportion of subjects with a microbiological success at the EOI (micro-ITT and ME-EOI populations) and TOC (micro-ITT and ME-TOC populations) visits for each pathogen isolated at baseline. Microbiologic response for levofloxacin resistant and ertapenem resistant baseline pathogens will also be presented.

For subjects with baseline pathogens obtained from blood culture (ie, for bacteremic subjects), microbiologic success by baseline pathogen will also be summarized separately for the micro-ITT population.

In addition, a table will list all subjects in each treatment group with at least 1 baseline pathogen obtained from blood culture, including the per subject clinical response, per subject microbiological response, and the per-pathogen microbiological response for each pathogen.

Per-pathogen microbiological success will also be summarized by baseline pathogen and MIC to study drug received for those pathogens with a sample size of at least 10 in 1 of the treatment groups in the micro-ITT population.

Microbiological categories for pathogens identified after baseline assessment are superinfection and new infection, which are defined as follows:

- Superinfection: Emergence of a new pathogen during therapy, from urine or blood cultures, with emergence or worsening of signs and symptoms of infection (ie, is determined by the Investigator to be a clinical failure)
- New infection: Emergence of a new pathogen after completion of therapy, from urine or blood cultures, with emergence or worsening of signs and symptoms of infection (ie, is determined by the Investigator to be a clinical failure)

The number and percentage of subjects with a superinfection or new infection after baseline will be presented by treatment group. A listing will be provided that presents the subjects with a superinfection and new infection including the type of specimen and pathogen.

Decreasing susceptibility of a pathogen is defined as continued presence of the baseline pathogen at $\geq 10^4$ CFU/mL with a > 2 -fold (at least 2 dilutions) increase from baseline to any subsequent study time point in the MIC of the study drug received. The number and percentage of subjects in the micro-ITT population with a pathogen showing decreasing susceptibility will be tabulated for each treatment group. In addition, a table will list all subjects in each treatment group with a pathogen showing decreasing susceptibility, including the type of specimen, pathogen, and MIC values for the drug received.

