11.1.4 Blood Cultures

Aerobic and anaerobic blood cultures will be obtained at two separate sterile venipuncture sites prior to initiation of clinical trial drug therapy. Upon knowledge of a positive culture for a pathogen, blood cultures should be repeated until sterile (i.e., both sets of cultures from two separate venipuncture sites are negative for pathogens) through the FU visit. If baseline cultures are negative, follow-up cultures should be obtained only if clinically indicated (e.g., signs and symptoms of persistence, relapse, or new infection).

These specimens will be cultured and the species will be identified by the local or regional laboratory. All purified pathogen(s) will be sent to a central reference laboratory for confirmation of species identification and antimicrobial susceptibility analysis, including to study drugs. Specific instructions for sample collection, processing, and shipment can be found in the laboratory manual(s) for this study.

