14.2.2 Per Pathogen Microbiological Outcomes

Per pathogen microbiological outcome will be determined for the Day 5, EOI, EOT, TOC, and FU visits. Outcomes will be classified as success, failure, or indeterminate/missing based on the microbiologic response definitions (Section 11.1.7).

All purified bacterial pathogens cultured from clinical specimens will be evaluated for susceptibility to study drugs and the emergence of resistance and overgrowth of non-susceptible organisms.

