3.1.4. Microbiological Intent-to-Treat (micro-ITT) Population

The micro-ITT population will consist of all subjects in the ITT population who have at least 1 baseline bacterial pathogen on culture of urine or blood that causes urinary tract infection against which eravacycline and ertapenem have expected antibacterial activity. As clinical breakpoints for eravacycline have not yet been determined, for the purpose of this analysis population, all baseline bacterial pathogens will be considered susceptible to eravacycline with the exception of *Pseudomonas* species. Analyses in this population will be presented in summary tables by the treatment arm to which the subject was randomized.

To be considered a baseline pathogen, both of the following must be met:

1. The organism must have been isolated from a suitable urine or blood specimen obtained between 36 hours prior to enrollment and the first dose of study drug). A suitable urine specimen is one collected from a clean-catch mid-stream urine specimen, a newly-placed urinary catheter (including urethral catheters, supra pubic catheters, and nephrostomy tubes), cystoscopy, supra pubic aspiration, or a properly disinfected collection port.
2. The baseline urine specimen must grow at least 1, but no more than 2 bacterial isolates at $\geq 10^5$ CFU/mL each (or at $\geq 10^4$ CFU/mL if obtained via suprapubic aspiration, new nephrostomy or cystoscopy). If more than 2 bacterial isolates are identified, the urine culture will be considered uninterpretable unless the specimen is obtained via suprapubic aspiration, nephrostomy tube newly placed or cystoscopy, 1 of the isolates comprises $\geq 80\%$ of the total growth (predominant), or 1 or more isolates are also isolated

simultaneously from a blood culture. In the second case, only the predominant organism will be considered a baseline pathogen. In the latter case, only organisms isolated simultaneously from the urine culture and the blood culture will be considered baseline pathogens.

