5.7.1. Primary Efficacy Analysis

The primary outcome measure is a responder outcome derived from both clinical response and microbiological response at the EOI and the TOC Visit in the micro-ITT population.

Clinical Response:

Clinical response is based on the Investigator Responses on the CRF and is not derived programatically. Clinical response is classified by the Investigator as cure, failure or indeterminate based on the following definitions:

- **Clinical Cure:** Clinical cure is defined as complete resolution or significant improvement of signs and symptoms of the infection such that no rescue/non-study antibacterial therapy is required to treat the cUTI that presented at study entry

- **Clinical Failure:** Subjects are classified as a clinical failure based on:
 - Death related to cUTI at any time point
 - Persistence of clinical symptoms of cUTI or new symptoms have developed
 - Initiation of rescue/non-study antibacterial drug therapy for cUTI
- **Indeterminate/Missing:** If the subject's outcome is neither clinical cure nor clinical failure, then the outcome should be listed as indeterminate/missing, including death where the cUTI is clearly noncontributory. If the Investigator did not complete an assessment or if the subject did not complete the study visit, the outcome is considered missing

Subjects who are assessed as a clinical failure at the EOT visit or beyond will have the failure carried forward to all subsequent visits.

Data for all subjects will be reviewed to ensure the Investigators are following the protocol defined criteria for clinical response and queries will be issued as needed to clarify any response that does not meet the protocol definition.

Microbiologic Response:

Per-subject microbiological response is defined as follows:

- **Microbiological success:**
 - Reduction of the baseline pathogen(s) to $<10^4$ CFU/mL
- **Microbiological failure:**
 - Blood cultures are positive for the baseline pathogen(s), or
 - Urine culture grows $\geq 10^4$ CFU/mL of the baseline pathogen(s)
- **Microbiological Indeterminate/Missing:** No interpretable urine culture data are available

The primary efficacy outcome is defined in [Table 5](#).

Table 5 Primary Efficacy Outcome

Primary Efficacy Outcome		
Clinical Response	Microbiological Response	Responder Outcome
Cure	Success	Responder
Cure	Failure	Non-responder
Cure	Indeterminate / Missing	Indeterminate
Failure	Success	Non-responder
Failure	Failure	Non-responder

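### The SAP's decreasing-susceptibility rule sets a colony-count threshold with no separate criterion for blood, so an MIC rise seen only in a blood isolate is not tabulated

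*SAP*

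**What the plan says.** SAP 5.7.3.5 opens its definition with "Decreasing susceptibility of a pathogen is defined as continued presence of the baseline pathogen at" and goes on to the threshold and the MIC condition. In full it requires "continued presence of the baseline pathogen at $\geq 10^4$ CFU/mL with a > 2 -fold (at least 2 dilutions) increase" in the MIC of the drug received, at any study time point after baseline. Two outputs follow. One is a table: "The number and percentage of subjects in the micro-ITT population with a pathogen showing decreasing susceptibility will be tabulated for each treatment group". The other lists the subjects concerned, "including the type of specimen, pathogen, and MIC values for the drug received".

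The pathogens in question can come from either source: SAP 3.1.4 speaks of a "baseline bacterial pathogen on culture of urine or blood". The two kinds of specimen are handled differently. Protocol 11.1.3 has urine quantified with a calibrated loop down to 10^3 CFU/mL. For blood, protocol 11.1.4 says "These specimens will be cultured and the species will be identified by the local or regional laboratory" and sends isolates to the central laboratory for susceptibility testing, but describes no count.

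The microbiological failure definition in SAP 5.7.1 reflects that difference. Its first limb is "Blood cultures are positive for the baseline pathogen(s), or", with no count attached. Its second limb is urine at 10^4 CFU/mL or more.

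Protocol 14.2.2 states the intention: "All purified bacterial pathogens cultured from clinical specimens will be evaluated for susceptibility to study drugs and the emergence of resistance". The Microbiology paragraph of the protocol summary names blood culture pathogens explicitly in the same connection.

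**The concern.** The decreasing-susceptibility rule keeps the count threshold that SAP 5.7.1 uses for urine and leaves out the blood limb. Applied literally by a programmer, it needs a CFU/mL value that the described blood procedure does not produce. A baseline pathogen that persists in blood with a raised MIC while the urine has fallen below the threshold would satisfy the blood criterion for failure and yet not appear in the resistance table. That table is the only tabulation in the SAP of post-baseline change in MIC. Events of this kind can be expected to be few, so an omission would be hard for a reader of the report to notice.

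**Working it through.** The plan states no figure to reproduce. The check sets the definitions side by side.

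**Inputs**

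- Counting rule: pathogen at 10^4 CFU/mL or more and an MIC rise of at least two dilutions (SAP 5.7.3.5).
- Urine: quantified, lower limit 10^3 CFU/mL (protocol 11.1.3). Since 10^3 < 10^4, the urine method can resolve the threshold.
- Blood: grown, identified, susceptibility-tested; otherwise treated as positive or sterile (protocol 11.1.4).
- Failure: blood positive, or urine at 10^4 CFU/mL or more (SAP 5.7.1).

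**MIC condition.** On a two-fold dilution scale the first step above 2-fold is 4-fold, and 4 = 2^2 is two dilutions. The two wordings of the MIC condition agree, so the problem lies only in the count.

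**Cases**, each with the baseline pathogen recovered after baseline and the MIC raised by at least two dilutions:

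| Finding | Failure criterion met (SAP 5.7.1) | Counted (SAP 5.7.3.5) |
|---|---|---|
| Urine 10^4 or more, blood negative | Yes, urine limb | Yes |
| Urine 10^4 or more with the rise, blood positive | Yes, both limbs | Yes, through urine |
| Urine below 10^4 or sterile, blood positive with the rise | Yes, blood limb | No |
| Urine not collected, blood positive with the rise | Yes, blood limb | No |

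In the last row the SAP's indeterminate category, which is worded for urine alone, could also be read to apply. Under either label the subject is not a responder.

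**Timing.** Once a culture is known to be positive, blood cultures are repeated until sterile (protocol 11.1.4). Post-baseline urine is first scheduled at Day 5 (protocol 11.1.3). An early repeat blood isolate may therefore have no concurrent urine count.

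**Other outputs.** The MIC distributions in SAP 5.4 cover baseline pathogens. Superinfection and new infection in SAP 5.7.3.5 concern new organisms, and those definitions do name both urine and blood. The table listing bacteremic subjects gives clinical and microbiological response, not change in MIC.

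**Scale.** The documents give no rate of bacteremia, of later positive blood cultures or of MIC rises. Purely as assumptions, take 5% to 10% of the 790 planned micro-ITT subjects as bacteremic at baseline, and 2% to 5% of those with any later positive blood culture:

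- 790 × 0.05 = 39.5 and 790 × 0.10 = 79 bacteremic subjects
- 39.5 × 0.02 = 0.8 and 79 × 0.05 = 4.0 with a later positive culture

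That is about 1 to 4 subjects, both arms together, before two further conditions: an MIC rise, and no qualifying urine culture. The subjects actually missed are an unknown fraction of these, possibly none.

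**The case against.** The strongest reply is that the table counts subjects, not isolates. A bacteremic subject whose urine still grows the pathogen at the threshold with the MIC rise is included. This stands. A reader might infer from the rule that a pathogen persisting in blood with a raised MIC can never be counted. The documents support only the narrower statement that it is not counted on the blood culture alone.

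Second, the protocol promises evaluation of blood isolates, and its summary places that evaluation at a central laboratory. It does not promise a summary table. This also stands, so the SAP breaks no explicit reporting commitment. The mismatch is between the SAP's own definitions, and between the rule and the protocol's evident intention.

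Third, the subjects remain visible elsewhere. They meet the failure criterion, bacteremic subjects are listed individually, and the Microbiology Review Committee sees post-baseline isolates (SAP 3.2.2). Raw MIC values may also appear in data listings. That limits the harm, but none of these outputs flags or counts a change in MIC.

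Fourth, no document says outright that blood cultures yield no count. It is inferred from the contrast between protocol 11.1.3 and 11.1.4 and from the count-free blood limb in SAP 5.7.1. The inference is reasonable.

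A reader might also infer that a rise in levofloxacin MIC goes untabulated, because SAP 5.4 lists levofloxacin apart from the study drug received. The documents do not establish this. SAP 5.6 treats study drug as both IV and oral, and the separate listing in SAP 5.4 concerns baseline isolates. The term is at most ambiguous, and no separate levofloxacin table is argued for here.

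**Conclusion.** The rule is wrong as written, at low severity. It omits persistence shown only in blood, although the SAP's failure definition recognises it and the protocol says blood pathogens will be evaluated for emergence of resistance. The listing's specimen-type field suggests that more than one kind of specimen was expected.

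The number affected is unknown and probably very small. The output is an additional descriptive table, and neither the responder outcome nor the non-inferiority test at EOI or TOC uses it. It would go too far to say that the reported arm counts will be materially distorted, since nothing in the documents supports a frequency. The event should also be described as the defined MIC rise rather than as resistance: SAP 3.1.4 notes that eravacycline breakpoints had not been set.

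The conclusion rests on a literal reading of the threshold and on blood being uncounted, as the described procedures imply.

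**What to change.** In SAP 5.7.3.5, define decreasing susceptibility as an MIC increase of at least two dilutions from baseline to the drug received, in a baseline pathogen that either (a) persists in urine at 10^4 CFU/mL or more, or (b) shows any growth in a post-baseline blood culture. This mirrors the two limbs of the failure definition in SAP 5.7.1. The table and listing keep their present layout, and the specimen-type field then distinguishes the two routes.

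The cost is one clause and one extra programming condition. Blood isolates already go to the central laboratory for susceptibility testing, so no new data are needed. If the SAP is already signed, the change belongs in an amendment before database lock, as SAP 1.1.1 provides.
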